6.8.2 Immune-effector Cell-associated Neurologic Syndrome
For this trial, ICANS will be using the criteria referenced in the publication by
Lee et al, 2019. While the grading system has been developed in large part from
CAR-T therapies, symptoms of ICANS may be shared among immune effector cellassociated therapies such as BiTE molecules. Although there may be a wide
range of symptoms associated with ICANS, subjects may have a stereotypic
course of a specific set of symptoms. The earliest manifestations of ICANS are
tremor, dysgraphia, mild difficulty with expressive speech (especially in naming
objects), impaired attention, apraxia, and mild lethargy.

Immune effector cell-associated neurologic syndrome grade is determined by the most severe event (eg, depressed level of consciousness, seizure, motor findings, raised intracranial pressure [ICP]/cerebral edema) not attributable to any other cause. Refer to the immune effector cell-associated encephalopathy (ICE) score below for grading of ICANS.

Immune Effector Cell-associated Encephalopathy (ICE) Assessment Tool

The ICE tool was designed to provide objectivity for the grading of multiple overlapping encephalopathy terms. The tool includes an element for assessing the receptive aphasia seen in these subjects. The total score that after assessing the following questions will be used as an input in the determination of the ICANS grade.

- Orientation: Orientation to year, month, city, hospital: 4 points
- Naming: ability to name 3 objects (eg, point to clock, pen, button): 3 points
- Following commands: ability to follow simple commands (eg, "Show me 2 fingers" or "Close your eyes and stick out your tongue"): 1 point

Protocol Number: 20200439

Date: 05 June 2024 Page 79 of 176

• Writing: ability to write a standard sentence (eg, "Our national bird is the bald eagle"): 1 point

• Attention: ability to count backwards from 100 by 10: 1 point

ICE Scoring

- 7-9, grade 1
- 3-6, grade 2
- 0-2, grade 3
- 0 due to subject unarousable and unable to perform ICE
- Assessment, grade 4

Table 6-5 ASBMT Immune Effector Cell-associated Neurotoxicity Syndrome (ICANS) Consensus Grading for Adults

Neurotoxicity Domain ^a	Grade 1	Grade 2	Grade 3	Grade 4
ICE score ^b	7-9	3-6	0-2	0 (subject is unarousable and unable to perform ICE)
Depression level of consciousness ^c	Awakens spontaneously	Awakens to voice	Awakens only to tactile stimulus	Subject is unarousable or requires vigorous or repetitive tactile stimuli to arouse. Stupor or coma
Seizure	N/A	N/A	Any clinical seizure focal or generalized that resolves rapidly or nonconvulsive seizures on EEG that resolve with intervention	Life-threatening prolonged seizure (> 5 min); or repetitive clinical or electrical seizures without return to baseline in between
Motor findings ^d	N/A	N/A	N/A	Deep focal motor weakness such as hemiparesis or paraparesis
Elevated ICP/cerebral edema	N/A	N/A	Focal/local edema on neuroimaging ^e	Diffuse cerebral edema on neuroimaging; Decerebrate or decorticate posturing; or Cranial nerve VI palsy; or Papilledema; or Cushing's triad

Protocol Number: 20200439

Date: 05 June 2024 Page 80 of 176

ASBMT = American Society for Blood and Marrow Transplantation; CTCAE = Common Terminology Criteria for Adverse Events; EEG = electroencephalogram; ICANS = immune effector cell-associated neurologic syndrome; ICE = immune effector cell-associated encephalopathy; ICP = intracranial pressure; N/A = not applicable.

- ^a Other signs and symptoms such as headache, tremor, myoclonus, asterixis, and hallucinations may occur and could be attributable to immune effector-cell engaging therapies. Although they are not included in this grading scale, careful attention and directed therapy may be warranted.
- ^b A subject with an ICE score of 0 may be classified as grade 3 ICANS if awake with global aphasia, but a subject with an ICE score of 0 may be classified as grade 4 ICANS if unarousable.
- ^c Depressed level of consciousness should be attributable to no other cause (eg, no sedating medication).
- ^d Tremors and myoclonus associated with immune effector cell therapies may be graded according to CTCAE v5.0, but they do not influence ICANS grading.
- e Intracranial haemorrhage with or without associated edema is not considered a neurotoxicity feature and is excluded from ICANS grading. It may be graded according to CTCAE v5.0. Source: Lee et al, 2019

Refer to the regional prescribing information or institutional guidelines (if not addressed in prescribing information) for additional information regarding standard of care therapy.

6.8.3 Neurologic Events

Please see **Table 6-6** for the management of adverse events related to neurological events. For subjects with suspected neurological events, samples may be collected for analysis after discussion with the Medical Monitor.

Table 6-6. Management of Adverse Events Related to Neurologic Events

Toxicity	Gradea	Instructions for Treatment Interruption and Restart	
Neurologic Events	3 ^b	 Interrupt tarlatamab until the event improves to grade ≤ 1 and administer corticosteroids per local practice 	
		Resume tarlatamab no less than 72 hours after the initial observation of the grade 3 adverse event at 1 dose level below	
		Permanently discontinue if:	
		o Initial grade 3 neurologic event does not improve to grade ≤ 1 within 7 days, OR	
		Grade 3 neurologic event reoccurs at the lower dose level within 7 days of re-initiation	
	4	Permanently discontinue tarlatamab	
	Seizure	Interrupt tarlatamab, administer corticosteroids and anti-seizure medication per local practice	
		For restart, refer to grade 3 neurologic events above for dose level rules for re-instituting infusion.	
		Do not re-initiate tarlatamab until 7 days after the last seizure and after therapeutic levels of anti-seizure medication are likely to have been achieved.	
		Permanently discontinue if a second seizure occurs with re-initiation of tarlatamab at any dose Private for Advance French (CTCAF) Suid-lines Version 4.0	

^a Per Common Terminology Criteria for Adverse Events (CTCAE) Guidelines Version 4.0

^b For adverse events grade ≤ 2, please follow institutional guidelines for management.

Protocol Number: 20200439

Date: 05 June 2024 Page 81 of 176

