6.2.2.1.3 Rules for Withholding or Restarting

Tarlatamab should be withheld for any of the following:

- DLT
- Symptomatic hypophysitis (See Section 6.8.4)
- Criteria for conditional withholding of tarlatamab due to potential hepatotoxicity (Section 11.7)

Tarlatamab dosing can be resumed if the toxicities resolve to grade \leq 1 or return to subjects' baseline values within 3 weeks. The restarting of therapy should be deemed safe by the investigator and medical monitor.

Subjects should not be restarted with tarlatamab if the following treatment-related adverse events occur:

- Criteria for permanent withholding of tarlatamab due to potential hepatotoxicity (Section 11.7)
- Any grade ≥ 4 adverse events except those not considered DLT as described in Section 6.2.1.4
- Grade 3 adverse event(s) that do not recover to grade ≤ 1 within 3 weeks
- Any grade 3 adverse events that recur (with the exception of grade 3 laboratory parameters not considered clinically relevant or recurrent non-febrile grade 3 neutropenia which resolves with supportive care to grade ≤ 1 or returns to subjects' baseline values within 3 weeks)

For adverse events related to CRS, neurological events and pituitary dysfunction, please see Sections 6.8.1, 6.8.3, and 6.8.4 respectively for guidelines for dose adjustment.

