9.1 Statistical Hypotheses

No formal statistical hypothesis will be tested.

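### A grade 4 seizure meets two rows of Table 6-6 with incompatible restart instructions, and restart after a late recurrence of a grade 3 neurologic event is not reconciled with Section 6.2.2.1.3

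*Protocol*

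**What the plan says.** **Table 6-6 (Protocol 6.8.3)** has three entries under neurologic events.

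- Grade 3: interrupt until recovery to grade 1 or lower, then "Resume tarlatamab no less than 72 hours after the initial observation of the grade 3 adverse event at 1 dose level below". Permanent discontinuation follows if the first event has not improved to grade 1 or lower within 7 days, or if a "Grade 3 neurologic event reoccurs at the lower dose level within 7 days of re-initiation".
- Grade 4: permanent discontinuation, with no exception.
- Seizure: interrupt and treat. For restart, use the dose-level rules of the grade 3 row, and "Do not re-initiate tarlatamab until 7 days after the last seizure". Permanent discontinuation comes only with a second seizure after re-initiation. No grade is given for this row.

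**Protocol 6.2.2.1.3** is the general rule on withholding and restarting. It states: "Subjects should not be restarted with tarlatamab if the following treatment-related adverse events occur". The list includes events of grade 4 or higher, apart from those that Section 6.2.1.4 does not count as dose-limiting. It also includes "Any grade 3 adverse events that recur (with the exception of grade 3 laboratory parameters not considered clinically relevant", with a further exception for non-febrile grade 3 neutropenia. The section ends by referring neurological events to 6.8.3 for dose adjustment.

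**Protocol 6.2.2.1.1 and 7.1** cap dose reductions at one per subject and list the need for more than one as a reason for removal from treatment.

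**Table 6-5 (Protocol 6.8.2)**, the ICANS scale, defines a grade 4 seizure: "Life-threatening prolonged seizure (> 5 min); or repetitive clinical or electrical seizures without return to baseline in between".

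**The concern.** A table of this kind should give one action for one event. Here a single event, a grade 4 seizure, can be read into two rows, one ending treatment and the other allowing it to resume. For a recurrent grade 3 neurologic event, the event-specific table carries a 7-day qualifier that the general rule lacks.

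The stake is mainly subject safety. Section 2.3.3.3 lists exacerbated neurologic events as a key risk of the combination. Enrollment ended in January 2023 (Protocol 4.1) and AMG 404 is no longer supplied as of Amendment 3 (Table 6-1). The June 2024 protocol nevertheless carries a tarlatamab monotherapy schedule (Table 1-2), so a decision to re-expose a subject can still arise.

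There is also a minor reporting effect. Adverse events leading to discontinuation are tabulated (Protocol 9.4.2.3.2, SAP 9.6.2), and those counts depend partly on which text is followed. They are descriptive only: Protocol 9.1 says that "No formal statistical hypothesis will be tested".

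**Working it through.** The documents state no figure on this point, so the check sets the texts side by side, case by case.

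| Case | Table 6-6 | Section 6.2.2.1.3 (treatment-related events) | Result |
|---|---|---|---|
| Grade 4 seizure, read by the grade 4 row | Permanent discontinuation | No restart | Agree |
| Grade 4 seizure, read by the Seizure row | Interrupt; re-initiation allowed; stop at a second seizure | No restart | Conflict, inside the table and with the general rule |
| Grade 3 recurrence at the lower dose, within 7 days | Permanent discontinuation | No restart | Agree |
| Grade 3 recurrence after 7 days | No instruction | No restart | Unreconciled |

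**Grade 4 seizure.** The Seizure row refers to the grade 3 row, but only for the dose level at restart; this does not limit which seizures enter the row. Seizure is not named among the exceptions in 6.2.1.4. A seizure attributed to tumor lysis syndrome might be argued into the exclusion there, but that would not settle which row of Table 6-6 applies. Section 6.8.2 grades ICANS but gives no tarlatamab interruption or restart rule, so Table 6-6 is the only seizure-specific instruction.

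**Grade 3 recurrence after 7 days.** Restart could come only by implication, from applying the grade 3 row again at one level lower. That would be a second reduction (1 + 1 = 2, against a cap of 1), which 6.2.2.1.1 does not allow and 7.1 lists as a reason for removal. The cap does not say whether treatment may resume at the already reduced level. If the bar in 6.2.2.1.3 applies in full, the 7-day qualifier does no work for treatment-related events. If the qualifier is meant to operate, late recurrence is handled differently from the general rule.

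**Which section governs.** Both texts claim restart: 6.2.2.1.3 by its title and Table 6-6 by its column heading. The pointer from one to the other mentions dose adjustment only. By comparison, 6.8.4 sends pituitary events back to 6.2.2.1.3 for restart, and 6.8.1 has its own rule, without a time window, for two grade 3 CRS events. Section 6.8.3 does neither. The question also reaches recovery time: for a grade 3 event to return to grade 1 or lower, 6.2.2.1.3 allows 3 weeks (21 days) and Table 6-6 allows 7 days.

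**Reach of the 7-day window.** After cycle 1 the schedules place tarlatamab in weeks 1 and 3 (Tables 1-2, 11-8 and 11-9), about 3 − 1 = 2 weeks apart. On that schedule the window covers only the first re-dose. This does not carry over to cycle 1, where Tables 11-5 to 11-7 show infusions in weeks 1, 2 and 3.

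**The case against.** On recurrence, a reader might infer that the two sections give opposite orders, with one allowing and the other forbidding restart after day 7. The documents do not support that. The 7-day line is itself a discontinuation trigger, Table 6-6 is silent afterwards, and silence is not permission. The reduction cap restricts the implied next step. It can also be argued that 6.2.2.1.3 is the general rule and 6.8.3 the specific one, since 6.2.2.1.1, 6.2.2.1.2 and 6.2.2.1.3 all refer neurological events there. Much of this stands. What remains is that no text says which rule yields on restart.

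On seizure, Table 6-6 grades by CTCAE version 4.0, whereas Table 6-5 is the ICANS scale, and the CTCAE seizure criteria are not in the documents. Table 6-5 therefore does not prove that a seizure is grade 4 for Table 6-6. That is fair, but it does not remove the overlap, because the Seizure row is not limited by grade on either scale. The pointer to the grade 3 rules may hint that lower grades were intended; the table does not say so.

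It would also overstate the matter to say that a site alone decides. Under 6.2.2.1.3 restart needs the judgment of the investigator and the medical monitor, and 6.2.2.1.1 adds the Global Safety Officer. That is a safeguard, but those people work from the same unreconciled text.

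**Conclusion.** The seizure point holds. As written, a grade 4 seizure has two incompatible instructions in one table, and the general rule agrees with only one of them. This assumes that a seizure can be grade 4 on the scale used for Table 6-6; the comparison with 6.2.2.1.3 also assumes a treatment-related event outside the exceptions in 6.2.1.4.

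The recurrence point holds only as a question of scope: the texts agree within 7 days, and afterwards they are unreconciled.

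No numerical size can be given, because the documents report neither the number of such events nor the number of subjects still on tarlatamab. No effect on the discontinuation tables has been shown, only a route to one. The correction should be made because it bears on re-exposure after a severe event and is simple to make. This review takes no position on which clinical rule is right.

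**What to change.** Reconcile the Seizure and grade 4 rows of Table 6-6 with each other and with 6.2.2.1.3, so that a grade 4 seizure has one stated action, and name the grading scale that decides it. State whether 6.8.3 or 6.2.2.1.3 governs restart for neurologic events, including grade 3 recurrence more than 7 days after re-initiation and the differing recovery times. Keep the result consistent with the reduction cap in 6.2.2.1.1 and the removal criterion in 7.1. The medical team must choose each rule.

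The cost is a protocol clarification letter or a few lines in the next amendment. No new data collection is needed.

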Skin	Grade 3 rash or suspected Stevens-Johnson syndrome (SJS) or toxic epidermal necrolysis (TEN)	Withhold	Administer corticosteroids at an initial dose of mg/kg/d prednisone (or equivalent) followed by taper. Treat	Monitor subjects for suspected severe skin reactions and exclude other causes (eg, infection, an effect of another drug, a skin condition linked to another systemic disease, etc.). For signs or symptoms of SJS or TEN, withhold study drug and refer the patient for specialized care for assessment and treatment.
	Grade 4 rash or confirmed SJS or TEN	Permanently discontinue	with topical emollients, oral antihistamines, and high-potency topical corticosteroids as indicated.	
Encephalopathy	Grade 2 (moderate symptoms, limited instrumental ADL)	Withhold	Administer corticosteroids at an initial dose of mg/kg/d prednisone (or	Monitor subjects for neurologic symptoms and exclude other etiologies (eg, infectious). Evaluation of patients with neurologic symptoms may include, but not be limited to, consultation with a neurologist, brain MRI, and lumbar puncture.
	Grade 3 or 4 (Severe symptoms; limiting self-care ADL; or life-threatening consequences; urgent intervention indicated)	Permanently discontinue (If event not attributable to tarlatamab)	equivalent) followed by taper. Consider empirical antiviral (IV acyclovir) and antibacterial therapy until CSF results obtained and negative for aseptic meningitis.	

Footnotes defined on last page of this table

Page 5 of 6

Protocol Number: 20200439

Date: 05 June 2024 Page 68 of 176

Table 6-2. AMG 404 Dose Modification and Toxicity Management Guidelines for Immune-Related Adverse Events

Immune-Related Adverse Reactions	Severity or Specific Conditions	AMG 404 Dose Modification	Management with Corticosteroids and/or Other Therapies	Monitor & Follow-up	
Myocarditis	Grade 1 (asymptomatic with laboratory [eg, BNP] or cardiac imaging abnormalities)	Withhold	initial dose of mg/kg/d call prednisone (or equivalent) syll followed by taper.	Monitor patients with cardiovascular symptoms. Ensure adequate evaluation to confirm etiology and/or exclude other causes.	
	Grade 2 (symptoms with mild to moderate activity or exertion)	Permanently discontinue			
	Grade 3 (severe with symptoms at rest or with minimal activity or exertion; intervention indicated)				
	Grade 4 (life-threatening consequences; urgent intervention indicated [eg, continuous IV therapy or mechanical hemodynamic support])	Permanently discontinue			

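### ICANS is graded on one scale with no tarlatamab action attached, while the only neurologic dose-action table uses another scale, and a grade 4 seizure meets opposite instructions

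*Protocol*

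**What the plan says.** **ICANS grade.** Protocol Section 6.8.2, added by Amendment 5, states "For this trial, ICANS will be using the criteria referenced in the publication by" a 2019 consensus paper, and instructs: "Refer to the immune effector cell-associated encephalopathy (ICE) score below for grading of ICANS". Table 6-5 then grades five domains: ICE score, level of consciousness, seizure, motor findings, and raised intracranial pressure or edema. The worst domain sets the grade. On management the section says only: "Refer to the regional prescribing information or institutional guidelines (if not addressed in prescribing information) for additional information regarding standard of care therapy". Section 2.3.3.1.1.2 sends the reader to 6.8.2 for ICANS guidance.

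**Dose actions.** Table 6-6 in Section 6.8.3 covers neurologic events. Footnote a to its grade column reads "Per Common Terminology Criteria for Adverse Events (CTCAE) Guidelines Version 4.0".

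- Grade 3: "Interrupt tarlatamab until the event improves to grade ≤ 1 and administer corticosteroids per local practice". Treatment then resumes at least 72 hours after onset, one dose level lower. It stops permanently if the event has not improved to grade 1 or less in 7 days, or recurs within 7 days of restart.
- Grade 4: permanent discontinuation.
- Seizure, with no grade attached: interruption, then restart under the grade 3 dose-level rules, no sooner than 7 days after the last seizure and once anti-seizure drug levels are likely therapeutic. It stops permanently after a second seizure.
- Grade 2 or lower (footnote b): institutional guidelines.

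**Routing.** Section 6.2.2.1.3 says: "For adverse events related to CRS, neurological events and pituitary dysfunction, please see Sections 6.8.1, 6.8.3, and 6.8.4 respectively". Sections 6.2.2.1.1 and 6.2.2.1.2 give the same three references. Section 6.2.2.1.3 also bars restart after treatment-related events of grade 4 or higher, apart from those that Section 6.2.1.4 does not count as DLTs.

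**General severity scale.** Section 11.4 grades every adverse event by CTCAE version 4.

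**The concern.** An investigator who diagnoses ICANS has to produce two grades: one from Table 6-5 and one from CTCAE version 4. Starting from Section 2.3.3.1.1.2, the investigator reaches Section 6.8.2 and obtains a grade that leads to no tarlatamab instruction. Starting from Sections 6.2.2.1.1 to 6.2.2.1.3, the investigator reaches Table 6-6, whose actions depend on the other grade and which never names ICANS. No sentence connects the two.

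The grade decides between management left to the institution, interruption with a lower dose, and permanent discontinuation. ICANS is also an event of interest in SAP Section 9.6.2, where such events are summarised by grade threshold and by whether they led to interruption, reduction or discontinuation. If the protocol does not settle which grade drives the action, those rows are harder to interpret: a discontinuation may reflect the severity of the event or the row the investigator chose.

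**Working it through.** No arithmetic applies. The check sets the passages side by side.

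**Step 1. Is there a tarlatamab action keyed to the ICANS grade?** No. Section 6.8.2 and Table 6-5 contain none. Interruption, reduction and discontinuation of tarlatamab by neurologic grade appear only in Table 6-6. For CRS, by contrast, Table 6-4 puts a syndrome-specific grade and the tarlatamab action in the same table.

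**Step 2. Are the two grades the same thing?** The protocol treats them as separate. Table 6-5 grades on five domains with its own thresholds. Its footnotes say that tremor and myoclonus may receive a CTCAE grade without influencing the ICANS grade, and that intracranial haemorrhage is left out of ICANS grading but may be graded by CTCAE. (Those footnotes cite version 5.0, not the version 4.0 used in Table 6-6.) A difference between the grades is therefore possible in either direction. Its size or frequency cannot be shown, because the CTCAE neurologic criteria are not reproduced in the documents.

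**Step 3. Is there a case where the text itself conflicts?** Yes: a life-threatening seizure lasting more than 5 minutes. Table 6-5 makes it ICANS grade 4. Its CTCAE v4.0 grade is not given in the documents, so each possibility is followed through.

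| Grade taken into Table 6-6 | Rows that apply | Restart of tarlatamab |
|---|---|---|
| ICANS grade 4 | Grade 4 row and Seizure row | Excluded by the first, possible under the second |
| CTCAE grade 4 | Grade 4 row and Seizure row | Excluded by the first, possible under the second |
| CTCAE grade below 4 | Seizure row (with the grade 3 dose-level rule) | Possible under stated conditions |

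In the first two lines Table 6-6 gives opposite instructions with no order of precedence. The third line differs from the first only in the scale used.

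**Step 4. Does Section 6.2.2.1.3 settle it?** Not clearly. Seizure is not among the exceptions listed in Section 6.2.1.4, so a treatment-related grade 4 seizure falls under the bar on restart. The same section then refers neurologic events to 6.8.3 for dose adjustment, where the Seizure row allows restart. It does not say whether 6.8.3 overrides the bar.

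**Step 5. Seizures below grade 4.** There is no comparable conflict. The Seizure row interrupts treatment whatever the grade and borrows the grade 3 dose-level rule.

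**The case against.** The best reply is that the governing scale is stated. Footnote a puts CTCAE v4.0 on Table 6-6, Section 11.4 uses the same family for all events, and the dose-modification sections send neurologic events to that table. Read literally, one table with one named scale gives one action, and the ICANS grade only describes the syndrome. This has force for events other than seizure. But nothing says that the ICANS grade is descriptive only. Section 6.8.2 sits among the risk-management guidelines for tarlatamab, and for CRS the protocol does let a syndrome scale drive dosing. The reply also leaves the seizure conflict in place, since that lies inside Table 6-6 and arises for a CTCAE grade 4 as well.

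A reader might infer something stronger: that the same event is grade 3 with interruption and a lower dose on one page, and grade 2 with no action on the next. The documents do not support this. No page ties interruption or reduction to an ICANS grade, and grade 2 or lower is referred to institutional guidelines, which is not the same as no action. A specific pair of discordant grades could be built only by borrowing the encephalopathy wording of Table 6-2. That table governs AMG 404, which Table 6-1 says is no longer supplied as of Amendment 3, and nothing shows that its wording is the CTCAE criterion Table 6-6 relies on.

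It is also fair to say that the reach is narrow. Enrollment ended in January 2023 (Section 4.1), and the ICANS section arrived with Amendment 5 in June 2024. That dose actions will vary between sites is a possibility, not something the documents show.

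**Conclusion.** The point holds as a missing link plus one explicit conflict. ICANS receives a grade with no tarlatamab action, the action table runs on a different grade that may not agree, and neither section mentions the other. For a life-threatening seizure of more than 5 minutes that is graded 4, the protocol gives both permanent discontinuation and conditional restart, and Section 6.2.2.1.3 does not resolve which applies.

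For an affected subject the difference is large: restart or permanent discontinuation of tarlatamab. Across the trial it cannot be sized. The number of ICANS events with discordant grades, and the number of grade 4 seizures, cannot be derived from the documents. The effect is confined to subjects still receiving tarlatamab and to the interpretation of dose actions already recorded. The conclusion assumes only that a grade 4 seizure can occur on treatment and that the two scales are distinct, as the footnotes to Table 6-5 treat them. It does not assume any particular CTCAE grade for any event.

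**What to change.** Reconcile Section 6.8.2 and Table 6-5, Table 6-6 and Section 6.2.2.1.3:

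- In footnote a of Table 6-6, state which grade triggers each row when the event is diagnosed as ICANS, and refer to Table 6-6 from Section 6.8.2.
- State which row takes precedence when a seizure is also grade 4, and say how that fits with the bar on restart in Section 6.2.2.1.3.
- Add 6.8.2 to the cross-references in Sections 6.2.2.1.1, 6.2.2.1.2 and 6.2.2.1.3.

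Which scale and which row should govern is for the sponsor's clinical team; no clinical rule is proposed here. The cost is one revised footnote, one precedence statement, one pointer in Section 6.8.2 and three cross-references, carried in a protocol amendment. No analysis method changes. When dose actions for ICANS are reported, a note on which grade governed them would help the reader.
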